9.4. Sample Size and Power Considerations

For Phase 1b, approximately 27 to 60 patients will be enrolled for up to 13 dose escalations of nanatinostat and valganciclovir and up to 10 patients in the exploratory proof-of-concept cohort of other EBV⁺ solid tumor patients.

The reported ORR for PD-1 inhibitors in RM-NPC patients has ranged from 20% to 30%. Assuming the pembrolizumab ORR in RM-NPC patients in this study will be around 25%, a sample size of 30 would provide a 95% confidence interval (CI) that excludes 10% as the lower ORR. A total of 60 patients (30 per randomized treatment group) is sufficient to provide adequate estimates of tumor response for each group and to provide initial indicators of safety and tolerability. These estimates will be utilized in planning for future studies in this patient population. The sample size of N=30 per randomized treatment group was determined from nQuery Advisor tool (www.statsols.com; Statistical Solutions, Ltd, Cork, Ireland).

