For Phase 1b, approximately 27 to 60 patients total will be enrolled during the dose escalation period. An additional 100 patients may be enrolled in Phase 2; up to 40 patients will be enrolled during the dose optimization cohort period and up to 60 patients in the dose expansion period with or without pembrolizumab. Up to an additional 10 patients total will be enrolled in the exploratory proof-of-concept cohort of other EBV⁺ solid tumors.

The reported ORR for PD-1 inhibitors in RM-NPC patients has ranged from 20% to 30%. Assuming that the pembrolizumab ORR for RM-NPC patients in this study will be around 25%, a sample size of 30 patients would provide a 95% CI that excludes 10% as the lower ORR. A total of 60 patients (30 per randomized treatment group) is sufficient to provide

	adequate estimates of tumor response for each group and provide initial indicators of safety and tolerability. These estimates will be utilized in planning for future studies in this patient population. The sample size of N=30 per randomized treatment group was determined using the nQuery Advisor tool (www.statsols.com; Statistical Solutions, Ltd, Cork, Ireland). Location: Global
Study Treatments, Dose, Route of Administration, Treatment Regimen	Nanatinostat (VRx-3996) oral – Starting dose: 20 mg once daily on Days 1 to 4 per week; Dose escalation: up to a total daily dose of 40 mg (Days 1 to 4 per week), then from 40 mg to 80 mg as a SDD twice daily 4 hours apart (Days 1 to 7) (RP2D to be determined during the
	Valganciclovir 900 mg oral once daily or twice daily for 21 days followed by a subsequent dose reduction to 900 mg once daily when administered with nanatinostat on Days 1 to 4 per week (intermittent dosing) and 450 mg twice daily when administered with nanatinostat on Days 1 to 7 per week (split daily dosing). (RP2D to be determined during the study)
	Pembrolizumab 200 mg IV every 3 weeks (See Section 3, Study Design for additional details on dosing regimens to be evaluated)
	For Phase 2 dose expansion, pembrolizumab will be administered initially 7 days after the start of nanatinostat and valganciclovir, and thereafter every 3 weeks. (Dosing schemas are provided in Section 5.3.3).
	Dosing Cycles : Cycle 1: 28 days. Cycles 2+: 21 days.

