Because PD-L1 is highly expressed by NPC cells and a correlation exists between tumor PD-L1 expression with shorter OS, recurrence-free survival, and treatment failure (Hsu 2010), antiprogrammed cell death-1 (PD-1) antibodies have been evaluated for the treatment of patients with RM-NPC. An ORR of 25.9% with a median PFS of 6.5 months was reported in a Phase 1b/2 trial (Keynote-028) in 27 patients with relapsed or metastatic PD-L1⁺ NPC treated with pembrolizumab (Hsu 2017). A Phase 2 trial evaluating nivolumab in 45 patients with RM-NPC who were not selected for PD-L1 expression reported an ORR of 20.5% (median PFS 2.8 months) (Ma 2018). More recently, an ORR of 20.5% with a median duration of response (DOR) of 12.8 months (median PFS of 1.9 months) was reported for a Phase 2 study of toripalimab, a humanized IgG4 monoclonal antibody against PD-1, in 190 patients with RM-NPC (Wang 2021). A decrease of 50% or more in the plasma EBV DNA copy number on Study Day 28 was associated with a significantly improved ORR (P=0.0001); tumor mutation burden had no predictive value for response. Therefore, combining a PD-1 inhibitor with EBV-targeted therapy may have the potential to augment anti-tumor activity for the treatment of RM-NPC.

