9.6.1. Primary Efficacy Endpoint Analysis

For Phase 2, the primary efficacy endpoint is the determination of ORR, defined as the percentage of patients with a CR or PR within the first 26 weeks (6 months) of treatment as

assessed by the Investigator using RECIST v1.1. ORR will be summarized by dosing regimen with 95% CI obtained by Clopper-Pearson Exact methods and stratified by prior anti-PD-1 treatment exposure.

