4.1.1 Reporting Conventions

The Phase 1b and Phase 2 portions of the study will be analyzed separately. Tables and figures will be summarized by dosing regimen. In general, all data collected, and any derived data will be presented in patient data listings, for all enrolled patients. Listings will be ordered by phase, site, patient number, treatment regimen, and assessment or event date. The dosing regimen presented in listings will be based on the planned assignment, unless otherwise noted.

In general, continuous variables will be summarized to indicate the study population sample size (N), number of patients with available data (n), mean, SD, median, first (Q1) and third (Q3) quartiles, minimum, and maximum values. Categorical variables will be summarized by the population size (N), number of patients with available data (n), number of patients in each category, and the percentage of patients in each category. Unless otherwise noted, and in order to determine the percentage of patients in each category, the denominator will be based on the number of patients with available data.

Select ordinal data may be summarized using both descriptive statistics and counts and percentages of patients in each category, as appropriate.

Non-zero percentages will be rounded to one decimal place. Rounding conventions for presentation of summary statistics will be based on the precision of the variable of summarization, as it is collected in its rawest form (i.e., on the electronic case report form [eCRF] or as provided within an external file) and are outlined as follows:

- The mean and median will be rounded to one more decimal place than the precision of the variable of summarization;
- Measures of variability (e.g., standard deviation, standard error) will be rounded to two more decimal places than the precision of the variable of summarization; and
- Minimum and maximum values will be presented using the same precision as the variable of summarization.

Other statistics (e.g., CIs) will be presented using the same general rules outlined above or assessed for the most appropriate presentation based on the underlying data.

No formal statistical analysis will be performed to compare treatment regimens. This study is exploratory in nature; descriptive statistics will be tabulated by treatment regimen and reviewed to evaluate all study endpoints.

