4.5.3 Primary Efficacy Endpoint Analysis Methods

Counts and percentages for each tumor response category assessed by the Investigator per RECIST v1.1 will be presented by dosing regimen. Separate summaries will also be produced by prior anti-PD-1 treatment exposure. Non-evaluable patients are considered non-responders and will be included in the denominator. ORR estimates, from the first post-baseline assessment, with corresponding binomial 95% confidence intervals using the Clopper-Pearson Exact method will also be presented.

For patients receiving pembrolizumab, the analysis will be repeated using iRECIST.

Results from tumor assessments will be provided in separate listings.

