4.5.5.5 Multiple Comparisons/Multiplicity

There will be no adjustments for multiple comparisons in the efficacy analysis for this study. Results are descriptive in nature, and there will be no formal comparisons made between treatment groups.

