4.8 Changes in the Conduct of the Study or Planned Analyses

Enrollment into Study VT3996-301 was discontinued after completion of the final Phase 1b dose level for business reasons unrelated to clinical factors or safety concerns. Patients who were receiving study drugs at the time of the study discontinuation notice continued to remain on study treatment as long as they derived clinical benefit, and they were to remain on study including and up to their final Safety Follow-Up Visit. Patients who were in the Long-Term Follow-Up period transitioned to End of Study. Reporting of serious adverse events continued per clinical study protocol Section 8.2.1.

Consequently, study conduct did not proceed to Phase 2 after the recommended Phase 2 dose of nanatinostat and valganciclovir was determined, and thus the Phase 2 study-specific analyses described in this SAP will not be performed. The study will be considered complete when all patients have completed safety follow-up assessments.

The only changes to the study conduct or planned analyses identified within the development of this SAP relative to the descriptions provided within the clinical study protocol are described below:

- Section 2 of the clinical study protocol only specified ORR as a primary efficacy endpoint for Phase 2, while ORR was added as a primary efficacy endpoint for Phase 1b in this SAP.
- Section 9.1 of the clinical study protocol states that all data will be summarized by dosing regimen, disease subtype, and overall, but data summaries by disease subtype are unnecessary since Phase 1b only enrolled patients with RM-NPC, and the study did not proceed to Phase 2.

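### Does 30 patients per arm really give a 95% CI that excludes 10% when the ORR is about 25%?

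*Protocol*

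**What the plan says.** Protocol 9.4 starts from published response rates of 20% to 30% for PD-1 inhibitors in RM-NPC. It assumes about 25% for this study and concludes that "a sample size of 30 would provide a 95% confidence interval (CI) that excludes 10% as the lower ORR". SAP 4.7 uses the same words, and the synopsis has "a sample size of 30 patients would provide a 95% CI that excludes 10% as the lower ORR". All three places then call 30 per randomized group sufficient for adequate estimates in each group and name nQuery Advisor as the source of N. None names the interval method behind the calculation, the number of responders needed, or the chance of reaching that number.

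The reporting method is named elsewhere. Protocol 9.6.1 specifies a "95% CI obtained by Clopper-Pearson Exact methods", and SAP 4.5.3 says that "corresponding binomial 95% confidence intervals using the Clopper-Pearson Exact method will also be presented".

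On the use of the results, SAP 4.1.1 says "No formal statistical analysis will be performed to compare treatment regimens" and SAP 4.5.5.5 says "Results are descriptive in nature, and there will be no formal comparisons made between treatment groups". SAP 4.8 records that "study conduct did not proceed to Phase 2 after the recommended Phase 2 dose of nanatinostat and valganciclovir was determined", and that the Phase 2 analyses will not be carried out.

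**The concern.** The sentence reads as if excluding 10% follows once the ORR is about 25%. With 30 patients, 25% is 7.5 responders, which is not an attainable count. The two nearest counts, 7 and 8, are equally far from 25% and almost equally likely, yet under the planned method they fall on opposite sides of 10%. A reader could take as assured something that is close to an even chance at the assumed rate, and about one in four at the low end of the range the protocol cites.

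This is the only quantitative support for 30 per arm, and the text says the estimates will feed the planning of later studies. If a go/no-go rule depended on excluding 10%, the missing count would matter. The wording also speaks of the ORR of pembrolizumab, although no arm receives pembrolizumab alone, so it is not clear which arm the 25% describes.

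**Working it through.** **Inputs.** n = 30 per group, planning ORR 25%, cited range 20% to 30%, rate to exclude 10%, two-sided 95% interval (Protocol 9.4, SAP 4.7). Interval method: Clopper-Pearson (Protocol 9.6.1, SAP 4.5.3). Published rates from Protocol 1.2.1: 25.9% ("An ORR of 25.9% with a median PFS of 6.5 months was reported in a Phase 1b/2 trial" of pembrolizumab) and 20.5% (nivolumab and toripalimab studies).

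**Formulas.** For x responders of n:

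- lower limit = 0.025 quantile of Beta(x, n − x + 1)
- upper limit = 0.975 quantile of Beta(x + 1, n − x)
- P(X ≥ 8) = Σ C(30, k) p^k (1 − p)^(30 − k), for k = 8 to 30

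**Step 1: the plan's own figure.** At x = 0.25 × 30 = 7.5 (interpolated), the exact limits are 11.09% and 44.10%. The lower limit is above 10%, so the claim reproduces. A Wilson interval also gives it (lower limit 13.0%). A Wald interval does not: 0.25 − 1.96 × √(0.25 × 0.75 / 30) = 9.5%. The stated result therefore agrees with the method the plan says it will use.

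**Step 2: attainable counts, n = 30.**

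| Responders | ORR | Exact 95% CI | Excludes 10%? |
|---|---|---|---|
| 6 | 20.0% | 7.7% to 38.6% | no |
| 7 | 23.3% | 9.93% to 42.28% | no, by 0.07 points |
| 8 | 26.7% | 12.28% to 45.89% | yes |
| 9 | 30.0% | 14.7% to 49.4% | yes |

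At a true ORR of 25%, P(X = 7) = 16.6% and P(X = 8) = 15.9%.

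**Step 3: chance of at least 8 of 30.**

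| True ORR | P(X ≥ 8) |
|---|---|
| 20% | 23.9% |
| 20.5% | 26.2% |
| 25% | 48.6% |
| 25.9% | 53.1% |
| 30% | 71.9% |

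**Step 4: dependence on exactly 30 analysed.** ORR is analysed in the Full Analysis Set, which requires a post-baseline tumor assessment (Protocol 9.3, SAP 4.2), so the denominator can be below 30. The SAP counts non-evaluable patients as non-responders, but that does not bring in patients who never enter the set.

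- 29 analysed: 7 responders suffice (lower limit 10.3%), with probability 61% at a true 25%.
- 28 analysed: 7 responders suffice (lower limit 10.7%), with probability 57%. Here 7 of 28 is exactly 25%.

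The threshold of 8 is therefore specific to a full set of 30. The narrow miss at 7 of 30 comes from the discreteness of the counts and does not show that N was miscalculated.

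**The case for a change.** The strongest case for a change is that the condition in the text is on an assumed rate, whereas the interval depends on an observed count, and here the threshold falls between the two counts nearest the assumed rate. Saying that 30 patients would provide the exclusion is then stronger than a 49% chance supports. A later team could copy the sentence believing that 30 patients at 25% secures it. Read as a power claim, 30 would be well short: from 30 upward, the first n with at least an 80% chance at a true 25% is 49 (10 responders, 82%). One sentence giving the count, the interval and the probabilities would cost almost nothing.

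The figures behind this argument all stand, and so does the remark that the responder count is missing. Three parts of it do not carry through. First, the sentence is conditional, since it opens with the assumption of about 25%, and quoting the expected interval at a planning value is an ordinary way to justify a sample for estimation. The plan states no power, and reading one into it sets a test the text did not claim to pass. Second, 8 responders and 49% hold only if all 30 are analysed. Third, nothing in the documents says that the 25% belongs to the pembrolizumab-containing arm. It follows directly from published PD-1 inhibitor rates and N = 30 is then applied to both groups, so one could ask which arm is meant but could not supply the answer.

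**Conclusion.** No change is needed. The statement is correct at its planning value under the planned method (exact lower limit 11.1% at 25%). What it omits is detail that a statistician can fill in from any exact binomial table: 8 of 30 excludes 10%, 7 of 30 misses by 0.07 points, and the chance of at least 8 is 24%, 49% and 72% at true ORRs of 20%, 25% and 30%.

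Supplying that detail would gain nothing for this trial. No decision rule uses 10%, no comparison between regimens is planned, and the exact intervals would be reported whatever the count. With Phase 2 not started, there are no randomized arms of 30 to which the sentence applies. SAP 4.8 does add ORR as a primary efficacy endpoint for Phase 1b, but the N = 30 reasoning was never about those dose cohorts of 3 to 6 patients.

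This rests on reading the sentence as a statement of expected precision, which its context of descriptive estimation supports, and on a two-sided 95% interval. Anyone who reuses the 30-per-arm rationale in a trial where excluding 10% drives a decision should work from the probabilities above and not from the sentence.

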9.5. Baseline Characteristics and Subject Disposition

Demographic and baseline (last non-missing observation prior to treatment) disease characteristics will be summarized by dosing regimen for the Safety population. Patients' age, height, weight, and continuous baseline characteristics will be summarized using descriptive statistics (N, mean, standard deviation, median, minimum, maximum), while age classification (\leq 65 or \geq 65 years), gender, ethnicity, histology, and other categorical variables will be provided using frequency tabulations (count, percent) by dosing regimen. Medical history data (coded by Medical Dictionary for Regulatory Activities [MedDRA] dictionary) will be provided in data listings.

Patient disposition (analysis population allocation, entered, discontinued, along with primary reason for discontinuation) will be summarized using frequency and percent for both treatment and follow-up phases. A summary of patients enrolled by site will be provided. Major protocol deviations will be summarized using frequency tabulations for the Full Analysis Set population. Corresponding patient listings will be provided as well.

9.6. Efficacy Analysis

Efficacy analyses will be performed on the Full Analysis Set and the mITT population.

As described in Section 7.4.1.2, tumor responses for efficacy analyses will be assessed using the Investigator per RECIST v1.1 (MRI or CT with contrast) and will involve all known or suspected disease sites.

9.6.1. Primary Efficacy Endpoint Analysis

For Phase 2, the primary efficacy endpoint is the determination of ORR, defined as the percentage of patients with a CR or PR within the first 26 weeks (6 months) of treatment as

assessed by the Investigator using RECIST v1.1. ORR will be summarized by dosing regimen with 95% CI obtained by Clopper-Pearson Exact methods and stratified by prior anti-PD-1 treatment exposure.

9.6.2. Secondary Efficacy Endpoints Analysis

Secondary efficacy endpoints will include DOR, disease control rate (DCR), PFS, and OS:

- **Duration of response** (DOR): defined as the interval from date of first observed CR or PR to the date of documented disease progression or death due to any cause, whichever occurs first. All patients who have not progressed will be censored at the last non-missing tumor assessment. Estimates of median DOR with 95% CI will be determined by dosing regimen using Kaplan-Meier methods.
- **Disease control rate** (DCR): defined as the percentage of patients having a CR, PR, or stable disease at any time during treatment, as assessed by the Investigator using RECIST v1.1. DCR will be summarized by dosing regimen with 95% CI obtained by Clopper-Pearson Exact methods.
- Progression-free survival (PFS): defined as the interval from the start of study drug treatment to the date of first documented disease progression or death from any cause, whichever occurs first. Responding patients and patients who are lost to follow-up will be censored at their last tumor assessment date. Estimates of median PFS with 95% CI will be determined by dosing regimen using Kaplan-Meier methods. The 95% CI around the PFS and OS rates at 12 months (56 weeks) will also be presented.
- Overall survival (OS): defined as the interval from the start of study drug treatment to date of death for any reason. Surviving patients and patients who are lost to follow-up will be censored at their contact date. Estimates of median OS with 95% CI will be determined by dosing regimen using Kaplan-Meier methods.

9.6.3. Exploratory Endpoints

All exploratory endpoints will be summarized by dosing regimen and overall.

9.7. Safety Analysis

Safety analysis will be based on all patients in the Safety population and will be summarized overall, by dosing regimen, and by any other relevant subgroup (eg, solid tumor type).

Study medication exposure will be summarized for each patient and tabulated by dosing regimen including duration of study medication, total dose taken, and dose reductions.

Adverse events, vital sign measurements, clinical laboratory measurements, and concomitant medications will be summarized overall and by dosing regimen. Tabulations and listings of values for dose holds, modifications, or discontinuations; vital signs; and laboratory safety evaluations will be presented.

Adverse events will be coded according to MedDRA and classified using the NCI CTCAE v5.0. The incidence rates of AEs will be tabulated by System Organ Class and Preferred Term. Subsets of AEs to be summarized include SAEs, events of all CTCAE grade severities, suspected

treatment-related AEs, and events that resulted in withdrawal of study medication. The most severe grade of each preferred term for a patient will be utilized for summaries of AEs by NCI CTCAE grade. All AEs with corresponding attributes will be displayed in a by-patient listing. Adverse events leading to death or to discontinuation from treatment, events classified as NCI CTCAE Grade 3 or higher, suspected treatment-related events, all deaths, and SAEs will also be displayed in by-patient listings separately.

Clinical laboratory results will be summarized descriptively by dosing regimen, which will also include a display of change from baseline. Laboratory values outside of the normal ranges will be identified. Clinically significant hematologic and non-hematologic laboratory abnormalities that meet Grade 3 or Grade 4 criteria according to the CTCAE will be listed and summarized. Graphical display of selective lab parameters over the course of study will be provided.

Vital sign measurements will be listed for each patient at each visit. Descriptive statistics for vital signs, both observed values and changes from baseline, will be summarized by dosing regimen.

9.8. Interim Analysis

No interim analysis is planned.

10. STUDY COMMITTEES AND COMMUNICATIONS

A Safety Monitoring Committee comprising of the study lead Investigators and the Sponsor Safety Team will monitor the safety of treatment throughout the study.

11. LABORATORY REQUIREMENTS

All study-related laboratory and clinical data gathered in this protocol will be stored in a password-protected database. All patient information will be handled using anonymous identifiers. Linkage to patients' study data is only possible after accessing a password-protected database. Access to the database is only available to individuals directly involved in the study.

A written document containing the name, location, certification number, and date of certification of the laboratory to be used for laboratory assays and those of other facilities conducting tests must be submitted to the Sponsor prior to initiating the study. This document should be returned along with the Form FDA 1572 or Statement of Investigator. The Sponsor must be notified if the laboratory is changed or if any additional laboratory is to be used.

